FHbp	factor H binding protein
GC	Neisseria gonorrhoeae
GC	Good Clinical Practice
GMFR	Geometric Mean Fold Rise
GMT	Geometric Mean Titer
HIPAA	Health Insurance Portability and Accountability Act
HIV	Human Immunodeficiency Virus
ICF	Informed Consent Form
ICH	International Conference on Harmonisation
ICMJE	International Committee of Medical Journal Editors
ICS	Intracellular Cytokine Staining
IDCRC	Infectious Diseases Clinical Research Consortium
IDES	Internet Data Entry System
IgA	Immunoglobulin A
IgG	Immunoglobulin G
IM	Intramuscular
IND	Investigational New Drug Application

List of Abbreviations (continued)

IRB	Institutional Review Board
ISM	Independent Safety Monitor
IUD	Intrauterine Device
JAMA	Journal of the American Medical Association
LLC	Limited Liability Corporation
MAAEs	Medically-Attended Adverse Events
MBC	Memory B Cell
MedDRA	Medical Dictionary for Regulatory Activities
MeNZB	New Zealand Meningococcal Group B Vaccine
mL	Milliliter
mm	Millimeter
N	Number (typically refers to participants)
NAAT	Nucleic Acid Amplification Test
NadA	Neisserial Adhesion A
NHBA	Neisserial Heparin Binding Antigen
NIAID	National Institute of Allergy and Infectious Diseases, NIH, DHHS
NIH	National Institutes of Health
NSAID	Non-Steroidal Anti-Inflammatory Drug
OMV	Outer Membrane Vesicle
PBMC	Peripheral Blood Mononuclear Cell
PI	Principal Investigator
PID	Pelvic Inflammatory Disease
PL	Platelet Count
PorA	Porin protein
PP	Per Protocol
PT	Prothrombin Time
RPR	Rapid Plasma Regain
SAE	Serious Adverse Event/Serious Adverse Experience
SAP	Statistical Analysis Plan
SBA	Serum Bactericidal Antibody
SDCC	Statistical and Data Coordinating Center
SMC	Safety Monitoring Committee
STI	Sexually Transmitted Infection
USP	United States Pharmacopeial Convention
VTEU	Vaccine and Treatment Evaluation Unit

List of Abbreviations (continued)

WBC	White Blood Count
WHO	World Health Organization

1. PREFACE

The Statistical Analysis Plan (SAP) for “Mucosal immune responses against *Neisseria gonorrhoeae* following meningococcal immunization in healthy young adults” (DMID Protocol 19-0015) describes and expands upon the statistical information presented in the protocol.

This document describes all planned analyses and provides reasons and justifications for these analyses. It also includes sample tables, listings, and figures planned for the final analyses. A separate report shell will be created for the interim immunogenicity analyses. Regarding the final analyses and Clinical Study Report (CSR), this SAP follows the International Conference on Harmonization of Technical Requirements for Registration of Pharmaceuticals for Human Use (ICH) Guidelines, as indicated in Topic E3 (Structure and Content of Clinical Study Reports), and more generally is consistent with Topic E8 (General Considerations for Clinical Trials) and Topic E9 (Statistical Principles for Clinical Trials). The structure and content of the SAP provides sufficient detail to meet the requirements identified by the FDA and ICH, while all work planned and reported for this SAP will follow internationally accepted guidelines published by the American Statistical Association and the Royal Statistical Society for statistical practice. This SAP also follows the FDA guidance regarding the COVID-19 public health emergency. 1. Contingency measures implemented to manage study conduct during disruption of the study as a result of COVID-19 control measures. 2. All participants affected by the COVID-19 will be highlighted. 3. Analyses and corresponding discussions that address the impact of implemented contingency measures. 4. Any protocol deviation due to COVID-19 will be documented.

This document contains four sections: (1) a review of the study design, (2) general statistical considerations, (3) comprehensive statistical analysis methods for immunogenicity and safety outcomes, and (4) a list of proposed tables and figures. Within the table, figure, and listing mock-ups (Appendices 1, 2, and 3). Any deviation from this SAP will be described and justified in protocol amendments and/or in the CSR, as appropriate. The reader of this SAP is encouraged to also review the study protocol for details on conduct of the study and the operational aspects of clinical assessments.

2. INTRODUCTION

Gonorrhea is a sexually transmitted infection (STI) caused by the gram-negative diplococcus *Neisseria gonorrhoeae* (GC). In 2012 the World Health Organization (WHO) estimated approximately 78 million new cases of gonorrhea globally[1]. In the United States, gonorrhea is the second most reported notifiable disease, with more than 550,000 cases reported in 2017. Rates of gonococcal disease have been steadily increasing since 2009 irrespective of age, sex, ethnic group, or geographic region.

Though gonococcal infections are curable with antibiotic therapy, antimicrobial resistance has become a global public health problem. The prevalence of resistance to multiple antibiotic classes has increased gradually since the 1940s,[1] and GC isolates with reduced susceptibility to current first-line therapy – ceftriaxone and azithromycin – have emerged.[2] Given the large and growing burden of disease, and the threat of untreatable gonococcal infections due to antimicrobial resistance, a safe and effective vaccine is urgently needed. Unfortunately, previous efforts to develop a gonorrhea vaccine have been largely unsuccessful.

Recently, a retrospective case-control study in New Zealand demonstrated 31% (95% confidence interval (CI), 21-39) effectiveness of an outer membrane vesicle (OMV) meningococcal group B vaccine (MeNZB) against incident gonorrhea.[3] The same group of investigators also reported 24% (95% CI, 1-42) vaccine effectiveness against hospitalization caused by gonorrhea.[3] Previous ecological studies had suggested a possible protective effect of OMV vaccines against gonorrhea in Norway[4] and Cuba.[5] Meningococcal OMV vaccines have been used successfully to control epidemic strains of *N. meningitidis* serogroup B.[6] These vaccines elicit serum bactericidal antibody (SBA) responses directed primarily against meningococcal strain-specific porin protein, PorA.[7] The precise mechanism of cross-protection conferred by meningococcal OMV vaccines against GC remains unknown.

A four component meningococcal serogroup B vaccine (Bexsero® or 4CMenB) was recently licensed for use in the United States and was given a category B recommendation by the Advisory Committee on Immunization Practices (ACIP) for use in adolescents and young adults aged 10- 25 years,[8] which is administered intramuscularly as a two dose-series, with the second dose given at least one month after the first dose.

4CMenB includes OMVs containing PorA serosubtype P1.4, as well as three recombinant protein antigens (neisserial adhesion A [NadA], factor H binding protein [FHbp] fusion protein, and neisserial heparin binding antigen [NHBA] fusion protein).[9] An analysis of gonococcal incidence following a 4CMenB vaccination campaign in one region of Quebec, Canada found a non-significant reduction in gonorrhea cases in the post-vaccination period,[10] supporting the findings from New Zealand, and suggesting that 4CMenB vaccine could protect against gonorrhea.

A recent study found a high level of amino acid sequence identity between the 4CMenB OMV antigens and those in the MeNZB OMV in the vaccine studied in New Zealand, and with OMV homologues in a laboratory strain of GC. The same study found that rabbits vaccinated either with MeNZB or the OMV component of 4CMenB raised antibodies against GC, and that 4CMenB vaccination in humans elicited serum antibodies against GC.[11] In contrast, another study found vaccination with a native OMV vaccine raised SBA responses against GC in mice, but 4CMenB vaccination did not elicit similar SBA responses in humans.[12]

Given the potential public health impact of an effective vaccine against gonorrhea, a better understanding of the immunologic responses to GC following 4CMenB vaccination is needed. Specifically, although two studies have characterized antibody responses against GC following 4CMenB in serum, gonorrhea is a mucosal disease. While there are studies looking at the ability of meningococcal serogroup B vaccines to

modulate human nasopharyngeal mucosal immunity to *N. meningitidis*, there are no data on the impact of 4CMenB on immunologic responses at the human mucosal surfaces where GC is typically encountered (urethra, rectum, cervix, and pharynx).

This is a mechanistic clinical trial to assess the systemic and mucosal immunogenicity of the multicomponent meningococcal serogroup B vaccine (4CMenB or Bexsero) against GC, using a placebo vaccine (normal saline) as a comparator, in healthy young adults.

2.1. Purpose of the Analyses

These analyses will assess the immunogenicity and safety of the multicomponent meningococcal serogroup B vaccine (4CMenB or Bexsero) against GC in comparison with a placebo vaccine (normal saline) and will be included in the clinical study report.

3. STUDY OBJECTIVES AND ENDPOINTS

3.1. Study Objectives

3.1.1. Primary Objective

- To characterize the rectal mucosal IgG antibody response to GC elicited by the 4CMenB vaccine as compared with the placebo vaccine (normal saline) in healthy adult participants.

3.1.2. Secondary Objective

- To characterize the serum IgG antibody response to GC elicited by the 4CMenB vaccine as compared with the placebo vaccine in healthy adult participants.
- To assess the safety and reactogenicity of 4CMenB in healthy adult participants.

3.1.3. Exploratory Objectives

- To characterize the vaginal mucosal IgG antibody response to GC elicited by the 4CMenB vaccine as compared with the placebo vaccine in healthy adult participants.
- To characterize the oropharyngeal mucosal IgG antibody response to GC elicited by the 4CMenB vaccine as compared with the placebo vaccine in healthy adult participants
- To characterize the serum IgA antibody response to GC elicited by the 4CMenB vaccine as compared with the placebo vaccine in healthy adult participants.
- To characterize the mucosal IgA antibody response to GC elicited by the 4CMenB vaccine as compared with the placebo vaccine in healthy adult participants
- To characterize the systemic B cell responses to GC antigens elicited by 4CMenB vaccine as compared with the placebo vaccine in healthy adult participants.
- To characterize the systemic T cell responses to GC antigens elicited by 4CMenB vaccine as compared with the placebo vaccine in healthy adult participants.
- To characterize the mucosal T cell responses to GC antigens elicited by 4CMenB vaccine as compared with the placebo vaccine in healthy adult participants.
- To characterize the serum bactericidal antibody responses to GC elicited by 4CMenB vaccine as compared with the placebo vaccine in healthy adult participants.
- To evaluate the impact of 4CMenB vaccine-induced antibodies on gonococcal adhesion to human cervical cells.
- To characterize immune responses to *N. meningitidis* elicited by the 4CMenB vaccine as compared with the placebo vaccine in healthy adult participants for use as controls.

3.2. Endpoints

3.2.1. Primary Outcome

- Rectal mucosal IgG concentrations (geometric mean titers, GMT) against GC OMV antigens at Day 1, 29, 43, 57, and 181 in each treatment group.

3.2.2. Secondary Outcomes

- Serum IgG concentrations (GMT) against GC OMV antigens at Day 1, 29, 43, 57, and 181 in each treatment group
- Frequency and severity of any AE related to 4CMenB immunization through the end of the study.
- Frequency of SAEs through the end of the study.

3.2.3. Exploratory Outcomes

- Rectal mucosal IgG concentrations (GMT) against GC antigens before and after vaccination in each treatment group
- Serum IgG concentrations (GMT) against GC antigens before and after vaccination in each treatment group
- Vaginal mucosal IgG concentrations geometric mean titer (GMT) against GC antigens before and after vaccination in female participants in each treatment group
- Oropharyngeal mucosal IgG concentrations (GMT) against GC antigens before and after vaccination in each treatment group
- Serum IgA concentrations (GMT) against GC antigens before and after vaccination in each treatment group
- Rectal mucosal IgA concentrations (GMT) against GC antigens before and after vaccination in each treatment group
- Vaginal mucosal IgA concentrations (GMT) against GC antigens before and after vaccination in female participants in each treatment group
- Oropharyngeal mucosal IgA concentrations (GMT) against GC antigens before and after vaccination in each treatment group
- Frequencies and function of memory B cells specific for antigens from GC before and after vaccination by ELISpot in each treatment group.
- Frequencies and function of peripheral blood T cells specific for antigens from GC before and after vaccination by ELISpot in each treatment group.
- Frequencies, phenotype, and function of peripheral blood CD4+ T cells specific for antigens from GC based on cytokine profile before and after vaccination by intracellular cytokine staining in each treatment group.
- Frequencies, phenotype, and function of peripheral blood CD8+ T cells specific for antigens from GC based on cytokine profile before and after vaccination by intracellular cytokine staining in each treatment group.
- Frequencies, phenotype, and function of rectal mucosal CD4+ T cells specific for antigens from GC based on cytokine profile before and after vaccination by intracellular cytokine staining in each treatment group.
- Frequencies, phenotype, and function of rectal mucosal CD8+ T cells specific for antigens from GC based on cytokine profile before and after vaccination by intracellular cytokine staining in each treatment group.

- Serum bactericidal antibody titers against GC before and after vaccination in each treatment group.
- Percent inhibition of gonococcal adhesion to human cervical cell line (ME180) by mucosal antibodies at Day 43 in each treatment group.
- Serum IgG concentrations (GMT) against *N. meningitidis* antigens before and after vaccination in each treatment group.
- Frequencies and function of memory B cells specific for antigens from *N. meningitidis* before and after vaccination by ELISpot in each treatment group.
- Frequencies and function of peripheral blood T cells specific for antigens from *N. meningitidis* before and after vaccination by ELISpot in each treatment group.
- Frequencies, phenotype, and function of peripheral blood CD4+ T cells specific for antigens from *N. meningitidis* based on cytokine profile before and after vaccination by intracellular cytokine staining in each treatment group.
- Frequencies, phenotype, and function of peripheral blood CD8+ T cells specific for antigens from *N. meningitidis* based on cytokine profile before and after vaccination by intracellular cytokine staining in each treatment group.

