3.3.2. Immunogenicity Outcomes

In the primary, secondary, and exploratory outcomes, the GMT for Enzyme-Linked Immunosorbent Assay (ELISA) will be calculated for Days 1, 29, 43, 57 and 181 for each treatment arm. The GMT is defined as:

$$GMT = \sqrt[n]{X_1 * X_2 * X_3 * \dots * X_n}$$

In practice, it is the equivalent of: $GMT = \text{Exp}\{[\log(X_1) + \log(X_2) + \dots + \log(X_n)] / n\}$

Where the X_1, X_2, \dots, X_n are the titers for each participant at a certain timepoint. A sample SAS code for calculating the geometric mean and the 95% confidence interval is shown below.

```
proc surveymeans  
  data=data geomean;  
  var variable;  
  run;
```

The geometric mean fold rise (GMFR) for ELISA titers will be calculated for Days 29, 43, 57, and 181 compared to baseline titer in each study arm. The fold change for each participant at each timepoint is calculated first by dividing the follow-up titer by the baseline titer, then the geometric mean and 95% confidence interval will be calculated for each treatment arm at each timepoint.

Similarly, the ratio of serum to mucosal (rectal, vaginal, and oropharyngeal) IgG will be calculated at each time point. The geometric mean and confidence interval will be calculated as above.

Percent inhibition of gonococcal adhesion to human cervical cell line by mucosal antibody is defined as:

$$100\% * [(Titer \text{ without mucosal antibody} - Titer \text{ with mucosal antibody}) / Titer \text{ without mucosal antibody}]$$

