- Frequencies and function of memory B cells and T cells from peripheral blood for GC and *N. meningitidis* antigens will be measured at each visit with ELISpot. The frequencies (cell count) will be reported. Frequencies and function of CD4+ and CD8+ T cells specific for GC and *N. meningitidis* antigens from peripheral blood, and GC antigens from rectal mucosae. These will be measured at each visit with ICS. Cell frequencies will be reported.
- Serum bactericidal antibody against GC and *N. meningitidis* will be measured and reported as geometric mean titer and 95% confidence interval for each time point for the two treatment arms.
- Inhibition of bacterial adhesion to a human cervical cell line (ME180) by mucosal antibodies will be measured by bacterial adhesion assay, and geometric mean titer and 95% confidence interval at each time point for two treatment arms will be reported.
- Other exploratory Immunogenicity outcomes measured by ELISA, ELISpot, and bacterial adhesion assays will be reported similarly.

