6. GENERAL STATISTICAL CONSIDERATIONS

6.1. General Principles

Unless otherwise specified, continuous variables will be summarized using the following descriptive statistics: n (non-missing sample size), mean, standard deviation, median, minimum and maximum. For some immunogenicity outcomes, the titers /frequencies will be summarized by geometric mean titer (GMT) /geometric mean titer frequencies and confidence interval (CI), fold change (rise or decline) from baseline will be calculated for the follow up immunogenicity outcomes. When calculating geometric mean, only non-zero values will be included. The frequency and percentages (based on the non-missing sample size) of observed levels will be reported for all categorical measures. Exact confidence intervals for binomial proportions will be computed for safety variables. In general, all data will be listed, sorted by Treatment group, and participant, and when appropriate by visit number within participant. All summary tables will be structured with a column for each Treatment in the order presented and will be annotated with the total population size relevant to that table/treatment, including any missing observations.

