8.3. Exploratory Outcome Analyses

For the exploratory outcomes, summaries of IgG antibody concentrations (GMT) at each time point and GMFR in each treatment group are shown in [Table 18](#), [Table 19](#), [Table 20](#), and [Table 21](#). Summaries of the ratio of serum to mucosal IgG GMT results will be presented in [Table 22](#) and [Table 23](#). Summaries of pairwise ratios of mucosal IgG concentrations among anatomical sites will be generated at each time point and presented in [Table 24](#) and [Table 25](#). Summaries of IgA antibody concentrations and serum bactericidal antibody (GMT) at each time point and GMFR for other exploratory outcomes are shown starting in [Table 26](#) and concluding with [Table 33](#). Serum Bactericidal Antibody GMT and GMFR will be presented in [Table 34](#).

Summaries of the frequency of antigen-specific immune cells will include the mean if data are reported as percentage, or geometric mean if data are reported as cell count per million cells. The corresponding 95% confidence interval as well as the median, minimum, and maximum values will be presented. Fold rise from baseline will be summarized by arithmetic, geometric mean^[2] or median. The summary of frequencies will be presented starting in [Table 35](#) and concluding with [Table 45](#). Figures depicting the GMT (IgG, IgA) or frequency (MBC, T cells) for each assay over time will be presented beginning with [Figure 10](#) and continuing through [Figure 39](#) (GMTs), and [Figure 74](#) to [Figure 87](#) (frequencies). Reverse cumulative distribution (RCD) plots will be presented with separate panels for each visit, and separate curves within each panel for

each study arm and overall. Antibody titers are shown beginning with **Figure 40** and continuing through **Figure 73**. Percent inhibition of gonococcal adhesion to human cervical cell line (ME180) by mucosal antibodies at day 43 in each treatment group will be show in **Table 46**. The results for each participant at each visit are listed in **Listing 11** through **Listing 22**.

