Same format for the following tables:

Table 43: Frequencies and Function of Rectal Mucosal CD4+ T Cells Specific for Antigens by Time Point and Treatment Group - ICS - Per-Protocol Population

Table 44: Frequencies and Function of Rectal Mucosal CD8+ T Cells Specific for Antigens by Time Point and Treatment Group - ICS - Immunogenicity Population

[note: The CD8 table should not contain IL17+ as cytokine]

Table 45: Frequencies and Function of Rectal Mucosal CD8+ T Cells Specific for Antigens by Time Point and Treatment Group - ICS - Per-Protocol Population

[note: The CD8 table should not contain IL17+ as cytokine]

Table 46: Percent Inhibition of Gonococcal Adhesion to Human Cervical Cell Line (ME180) by Mucosal Antibodies at Day 43

Population	Assay	Percent Inhibition (95% CI)	
		4CMenB	Placebo
Immunogenicity Population	N*	x	x
	BAA_1291	x(x , x)	x(x , x)
	BAA_20	x(x , x)	x(x , x)
Per-Protocol Population	N*	x	x
	BAA_1291	x(x , x)	x(x , x)
	BAA_20	x(x , x)	x(x , x)

*N =Number of participants in the certain Treatment Group for certain analysis population

Table 47: Summary of Categorical Sexual History Variables at Screening - All Enrolled Participants

Variable		Characteristic	4CMenB N=X		Placebo N=X		All Participants	
			n	%	n	%	n	%
Oral receptive	Yes/No	No	x	x	x	x	x	x
		Yes	x	x	x	x	x	x
	How often did the participant or the participant's partner use a condom or barrier for protection?	Always	x	x	x	x	x	x
		Sometimes	x	x	x	x	x	x
		Never	x	x	x	x	x	x
Oral active	Yes/No	No	x	x	x	x	x	x
		Yes	x	x	x	x	x	x
	How often did the participant or the participant's partner use a condom or barrier for protection?	Always	x	x	x	x	x	x
		Sometimes	x	x	x	x	x	x
		Never	x	x	x	x	x	x
Rectal receptive	Yes/No	No	x	x	x	x	x	x
		Yes	x	x	x	x	x	x
	How often did the participant or the participant's partner use a condom or barrier for protection?	Always	x	x	x	x	x	x
		Sometimes	x	x	x	x	x	x
		Never	x	x	x	x	x	x
Rectal insertive	Yes/No	No	x	x	x	x	x	x
		Yes	x	x	x	x	x	x
	How often did the participant or the participant's partner use a condom or barrier for protection?	Always	x	x	x	x	x	x
		Sometimes	x	x	x	x	x	x
		Never	x	x	x	x	x	x
Genital/vaginal	Yes/No	No	x	x	x	x	x	x
		Yes	x	x	x	x	x	x
	How often did the participant or the participant's partner use a condom or barrier for protection?	Always	x	x	x	x	x	x
		Sometimes	x	x	x	x	x	x
		Never	x	x	x	x	x	x

Note: N is the number of participants answered "Yes" to the question "Sexual intercourse in last 6 months?"

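### SAP 4.5.1 calls for a geometric mean titer of adhesion inhibition at every time point, which conflicts with the Day 43 percent-inhibition endpoint and would drop no-effect participants

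*SAP*

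**What the plan says.** The objective in SAP 3.1.3 is "To evaluate the impact of 4CMenB vaccine-induced antibodies on gonococcal adhesion to human cervical cells". The matching endpoint in SAP 3.2.3 is "Percent inhibition of gonococcal adhesion to human cervical cell line (ME180) by mucosal antibodies at Day 43 in each treatment group", and SAP 8.3 sends the same Day 43 quantity to Table 46. That shell shows percent inhibition with a 95% CI by arm for two strains. It names no estimator and has no column for a difference between arms.

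SAP 3.3.2 defines the variable as 100% times (titer without antibody minus titer with antibody), divided by titer without antibody. The reference is a no-antibody condition, not the participant's own Day 1 specimen.

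SAP 4.5.1 treats the assay twice. Its opening text has percent inhibition by mucosal antibodies at Day 43. A later bullet on adhesion inhibition says that "geometric mean titer and 95% confidence interval at each time point for two treatment arms will be reported". SAP 6.1 adds a general rule: "When calculating geometric mean, only non-zero values will be included".

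Protocol 7.2.2.3 says that serum is collected for the adhesion assay. The endpoint, in protocol 3.3.3 and SAP 3.2.3, refers to mucosal antibodies.

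**The concern.** The SAP 4.5.1 bullet is the only place where an estimator is named for this variable in particular, and that estimator does not suit it. A percentage is not a titer, only one time point is planned, and the values that a geometric mean cannot take are the ones expected where antibody has no effect.

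A programmer who follows the bullet together with SAP 6.1 would lose those values. If the vaccine works, more would go from placebo, an inert placebo arm would look inhibitory, and the arm difference would shrink. The remaining placebo mean would rest on fewer than the planned 10 or so participants. This is the trial's functional read-out of whether antibody blocks adhesion, so a distorted summary could mislead even though the endpoint is exploratory.

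**Working it through.** The documents give no mean, SD, power or precision figure for the adhesion assay, so there is no stated figure to reproduce. The check sets the texts against each other and then illustrates the size of the problem.

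**1. The texts side by side.**
- Scale: percent inhibition in SAP 3.2.3, 3.3.2, the opening text of 4.5.1, 8.3, Table 46 and Listing 22; geometric mean titer in the 4.5.1 bullet.
- Time: Day 43 in SAP 3.2.3, the opening text of 4.5.1, 8.3, Table 46 and the title of Listing 22; every time point in the 4.5.1 bullet.
- Specimen: mucosal antibodies in the endpoint; serum in protocol 7.2.2.3.

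**2. Can inhibition be zero or negative?** Put illustrative titers into the SAP 3.3.2 formula, with 100,000 without antibody.
- 60,000 with antibody: 100 × (100,000 − 60,000)/100,000 = 40%.
- 100,000 with antibody: 0%.
- 120,000 with antibody: −20%.

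Neither 0 nor −20 has a logarithm. SAP 6.1 excludes the first and says nothing about the second.

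**3. What a geometric mean over the remaining values would report.** Assumptions: inhibition is normal within an arm and capped at 100, with SD 15 or 25 points; zeros and negatives drop out. Results from 2,000,000 simulated values per row:

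| True mean | Lost, SD 15 | Geometric mean, SD 15 | Lost, SD 25 | Geometric mean, SD 25 |
|---|---|---|---|---|
| 0 | 50% | 7.9 | 50% | 13.3 |
| 10 | 25% | 11.7 | 34% | 16.7 |
| 20 | 9% | 17.9 | 21% | 21.3 |
| 30 | 2% | 26.5 | 12% | 27.4 |

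Apparent arm differences:
- True 20 against 0 (a 20-point difference): 17.9 − 7.9 = 10.0 with SD 15; 21.3 − 13.3 = 8.0 with SD 25.
- True 30 against 10 (also 20 points): 26.5 − 11.7 = 14.8 with SD 15; 27.4 − 16.7 = 10.7 with SD 25.

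The second pair shows that the shrinkage is smaller when the placebo mean is above 0. The arithmetic mean of all values recovered the true mean in each row of the table.

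**4. What the Day 43 contrast offers without a baseline.** For 40 and 10 participants, the 95% half-width in SD units is t(0.975, 48) × √(1/40 + 1/10) = 2.01 × 0.354 = 0.71. The difference detectable with 80% power at two-sided 5% is (1.96 + 0.84) × 0.354 = 0.99 SD. At 30 and 6, the smallest size in protocol Table 2, these become 0.91 and 1.25 SD.

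Adjusting for a Day 1 value multiplies the standard error by √(1 − r²). With assumed r of 0.3, 0.5 and 0.7, the 40/10 half-width goes from 0.71 to 0.68, 0.62 and 0.51 SD.

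**The case against.** The best defence is that the geometric mean is not the settled analysis. It stands in one bullet, while the formula, the analysis text, the table shell and the listing all use percent. The SAP 6.1 default for continuous variables includes the arithmetic mean, and SAP 8.3 uses the mean for cell frequencies reported as percentages. The bullet might even refer to the titers inside the formula, which can be logged when positive. This stands to the extent that the fault is an internal inconsistency and not a firm plan to analyse wrongly. It does not remove the need for correction. The SAP 6.1 default yields to a specific instruction, the bullet is that instruction, and no table or listing is provided for the component titers.

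Two stronger readings are tempting, and the documents support neither.
- A reader might infer that, without a Day 1 value, the endpoint cannot show what vaccine-induced antibody did. Both arms are assayed at Day 43, allocation is randomised, and laboratory staff are blinded (SAP 4.1 and 4.4.5). SAP 4.2 gives the placebo arm exactly this role of attribution. Pre-existing antibody is balanced in expectation, so the between-arm difference is a valid estimate. What a missing baseline costs is precision and within-person change. The 4CMenB column read alone cannot be credited to the vaccine.
- A reader might infer from protocol Table 2 that most Day 43 inhibition predates vaccination, because the Ng OMV ratio is 34,297/42,224 = 81%. That is serum binding IgG, not inhibition by mucosal antibody, and it is the highest ratio in the table: Ng whole cell gives 48,503/78,793 = 62% and Ng rNHBA 34,297/1,176,267 = 3%. It also sits badly with a placebo mean of 0, the case in which the shrinkage above is largest.

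**Conclusion.** The concern holds as a conflict within the SAP over the scale and time points of one exploratory endpoint, with a named estimator that is wrong for the variable. Followed as written, that estimator would turn a true 20-point difference into about 8 to 10 points if the placebo mean is 0, or about 11 to 15 if the means are 10 and 30. These sizes rest on an assumed normal shape, assumed SDs of 15 to 25 points, and negatives being dropped along with zeros. The direction needs only that no-effect values are lost more often from the arm with less inhibition.

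The Day 43 randomised contrast is valid without a baseline, though imprecise with about 10 placebo participants. Table 46 does not yet report it. The impact is limited: the endpoint is exploratory, no formal test is planned, and SAP 6.2 places exploratory results in an addendum to the study report.

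**What to change.** **Required, wording and table shell only.**
- In SAP 4.5.1, replace the bullet with the arithmetic mean of percent inhibition at Day 43 with its 95% CI by arm, and state that zero and negative values are kept. An alternative is 100 × (1 − geometric mean of the ratio of titer with to titer without antibody). It also keeps them, but needs a rule for a ratio of zero.
- State in SAP 6.1 or 8.3 that the non-zero rule does not apply to percent inhibition.
- Add the 4CMenB-minus-placebo difference with 95% CI to Table 46.
- Reconcile protocol 7.2.2.3 (serum) with the endpoint (mucosal antibodies), and name the mucosal site if mucosal is meant. Protocol Appendix B has no row for this assay, and Listing 22 has a third strain column that Table 46 lacks. Align these in the same edit.

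**Optional.** Assay Day 1 specimens and use the value as a covariate. The gain is the factor √(1 − r²) on the standard error, with r unknown for this assay. The cost is one extra assay per participant and strain, plus Day 1 material that other assays also need; the SAP already makes several mucosal assays conditional on specimen availability. This should wait until the specimen type is settled.
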